7.3 Group B Follow-Up Schedule of Events (Treatment)

Evaluation	Day 7	Day 8- 13	Day 14 ± 4 Days	Day 28 ± 4 Days	Day 84 ± 4 Days
Evaluation location	Remote	Remote	Remote		Remote
COVID-19 symptom screen (8.1) (Phone, Emocha, or In-Person)	X	X	X		
Household survey ^(8.16)			X		
Administration of Flu-PRO Questionnaire ^(8.4)	X	X	X		
Concomitant medications ^(8.5)	X	X	X		
Limited Vital Signs ^(8.7) (T, RR, PoX)	X	X	X		
Upper respiratory specimens for SARS-CoV-2 assessment ^(8.11)	X	X ^a	X		
Serology for SARS-CoV-2 ^(8.12)					
Blood for Exploratory Testing ^(8.14)					
Adverse Event Monitoring ^(8.15)	X	X	X		
Contraception Remote Follow-Up ^(8.17)					X ^b

^a Home sampling for Group B participants Days 9, 11, and 13 if available. Frequency of collection is limited by shortages and infection control considerations.

^b For participants who, at screening, are females of childbearing potential or males with female partners of childbearing potential

8. Study Procedures

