8.12. Serology for SARS-CoV-2

At entry and day 28, all participants will have blood sampled to detect antibodies against the SARS-CoV-2 spike protein (S1 subunit). Testing will be performed at the Johns Hopkins Pathology Laboratory using the commercial Euroimmun antibody assay according to the manufacturer's recommendation. This assay has been validated by the Johns Hopkins laboratory. 6 mL of blood will be collected for each timepoint.

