Participants who are found to be infected with SARS-CoV-2 at baseline (Group B) or who become infected during the course of the study (Group A) will not return to the study site until Day 28 or until criteria for discontinuation of infected status is met per HEIC standards, whichever occurs later. In the event that an interim in-person visit is required to evaluate an adverse event, these participants may be seen in an ambulatory setting equipped for encounters with SARS-CoV-2 infected persons. In the event that participants become hospitalized, study evaluations that coincide with clinical care will be abstracted from the medical record. Research-specific evaluations will not continue in the inpatient setting.

11. Risks and Benefits

Potential Risks of Treatment

Identified risks associated with treatment with Lambda based on nonclinical and/or clinical data, as well as potential class effects, include hepatobiliary toxicity (transaminase elevations with or without hyperbilirubinemia) and injection site reactions; potential risks include neuropsychiatric disorders (including depression), cardiovascular events, immunogenicity/hypersensitivity reactions, autoimmune disorders, elevated amylase/lipase, dermatitis, hypersensitivity reaction, injection site reaction, and reproductive risk. Complete information on preclinical and clinical safety data is located in the Investigator Brochure.

Potential Benefits of Participation

Potential benefits include prevention of infection with SARS-CoV-2 infection or reduction in severity of COVID-19 symptoms. It is not yet known whether Lambda will have any benefit in this population.

Alternatives to Participation

The alternative to participation in this study is routine care and monitoring following close contact with an individual with COVID-19.

12. Outcome measures

12.1 Group A Prevention cohort primary endpoint:

- No evidence of SARS-CoV-2 infection at or before study day 28

For the purpose of the study endpoint, SARS-CoV-2 infection is defined as any of the following outcomes:

1. SARS-CoV-2 detected in upper respiratory samples at any of day 7, day 14 or day 21; or
2. New finding of serum antibodies (IgA or IgG) against the SARS-CoV-2 spike protein according to validated specifications and performance characteristics at or prior to day 28.

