13.1 Sample Size and Power Considerations

The planned sample size for the trial is 164 participants enrolled and randomized in a 1:1 ratio to lambda interferon-1a versus placebo injection. This sample size is based on the expectation that approximately 32.5% of participants who are enrolled have evidence of SARS-CoV-2 at study entry (an intermediate value consistent with the 25 – 40% infection range that we expect for the study outcome in the placebo group), thus around 110 will be will have no evidence of SARS-CoV-2 infection (Prevention Cohort) at enrollment and around 54 participants will have evidence of SARS-CoV-2 infection (Treatment Cohort). The Treatment Cohort represents an exploratory pilot study to provide estimates of antiviral efficacy for early COVID-19. Power estimates for the study are based on the Prevention Cohort and incorporate the following assumptions (multiple credible scenarios are presented):

The primary analysis for the efficacy/prevention of infection with SARS-CoV-2 in the Lambda interferon-1a and the placebo groups using proportional odds model and a two-sided Type I error rate (α) of 0.05. Since participants in both the Prevention and Treatment Cohorts will be dosed after entry, we anticipate that few, if any participants will not start treatment and be excluded from the primary analysis. Further, given the nature of COVID-19, we anticipate low rates of loss to follow-up before the primary endpoint (Day 14). We expect the incidence of new COVID-19 in the placebo group to be between 25% to 40%, thus we will perform calculation for these edge-case scenarios. In addition, we will be offering enrollment to all adults in a household (~2 per household), our analysis sample will be clustered-correlated by household. However, there is no preliminary or published data to model within-cluster correlation. Thus we are modeling scenarios where the effective sample size is as high as 110 individuals, or as low as the number of households of 55. In all scenarios, we are expecting that the cumulative infection fraction for the lambda interferon will be 5%.

Cumulative Infection Percentage in Placebo	Effective sample size	
	N= 110 individuals	N = 55 family clusters
25%	80.1%	36.1%
40%	99.6%	84.0%

We note that we have 80% or greater power (and Type II error rate beta of 0.2 or smaller) in a large range of scenarios.

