13.2 Statistical Analysis

13.2.1 Analyses will include all randomized participants Our primary analysis for both the prevention and treatment cohorts (outcomes of non-infection and resolution, respectively) will be mixed model logistic regression correcting for within-household correlation as a random effect. In addition to the placebo cumulative infectivity and odds ratios, we will express the overall

cumulative incidence of infection and the difference between lambda interferon vs. placebo using nonlinear combination (i.e., inverse logit of the placebo and active treatment groups and the difference of these after the inverse logit transformation). Statistical inference will use a two-sided Type 1 error rate of 0.05 and 95% confidence intervals.

For the exploratory treatment cohort, we will similarly examine clearance of infection.

In addition, we will perform survival analysis for time to infection in the prevention cohort and time to infection clearance in the treatment cohort, modeling within cluster correlation of hazard as a random effect (frailty).

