13.2.2 Analysis of Secondary outcomes including adverse events

For secondary time to event outcomes, we will perform survival analysis for time to infection in the prevention cohort and time to infection clearance in the treatment cohort, modeling within cluster correlation of hazard as a random effect (frailty).

Analysis of AE data will primarily be descriptive based on MedDRA coding of events. The proportion of participants experiencing an SAE and the proportion experiencing a Grade 3 or higher. AE will be compared between randomized arms using Fisher's Exact Test. Statistical analyses for the InFLUenza Patient-Reported Outcome (FLU-PRO[®]) measure of ordinal data of independent groups with more than three samples will utilize the Kruskal-Wallis H method.

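### Time to infection and time to clearance are interval-censored, but the planned frailty hazard analysis has no interval-censoring, tie or event-date rule; the effect is material mainly in Group B.

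*Combined protocol and SAP*

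**What the plan says.** Sections 13.2.1 and 13.2.2 both state that "we will perform survival analysis for time to infection in the prevention cohort and time to infection clearance in the treatment cohort". Each section then says how households enter the model, namely by "modeling within cluster correlation of hazard as a random effect (frailty"). In 13.2.1 this supplements the mixed-model logistic primary analysis. In 13.2.2 it is the whole specification for secondary time-to-event outcomes. Neither section names a baseline hazard, a tie method, interval-censoring or a rule for the event date. Time to resolution in the treatment cohort is objective 3.3.2.4.

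When the events can be seen:

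- **Group A swabs.** None before Day 7 (7.1, footnote b), then Day 7 and Day 14 ± 4 (7.2). Section 8.11 adds Day 28 for those who stay asymptomatic; 12.1 defines infection by Days 7, 14 or 21. Participants with symptoms are referred for clinical testing (8.11), and 12.1 does not say whether those results count.
- **Antibody.** "At entry and day 28, all participants will have blood sampled to detect antibodies against the SARS-CoV-2 spike protein" (8.12).
- **Group B swabs through Day 14.** Day 7 and Day 14 ± 4 carry no condition. The others do: "Home sampling for Group B participants Days 9, 11, and 13 if available" (7.3), with the same condition for Days 2, 4 and 6 (7.1). Both footnotes cite shortages and infection control.
- **Clearance.** 12.2 requires two non-detections by Day 14 and does not say which of them dates the event.
- **Hospitalization.** "Research-specific evaluations will not continue in the inpatient setting" (section 10), although the sentence before it allows evaluations that coincide with clinical care to be abstracted.

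**The concern.** An infection or clearance is known only to lie between two tests. If the visit day is entered as the event day, many participants share the same few event times, and the hazard ratio then depends on a software option that the plan does not fix. In Group B the recorded clearance day also depends on how often a participant was swabbed, so a difference in swabbing between arms would look like a difference in clearance. In Group A, an infection found only by the Day 28 antibody test has no known day. At stake is a named Group B objective, and an analyst's choice that should be closed before results are seen.

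**Working it through.** **1. The plan's own figures.** Section 13.1 plans for "164 participants enrolled and randomized in a 1:1 ratio" with a "two-sided Type I error rate (α) of 0.05". A two-sided Fisher exact test with lambda at 5% infected, at 55 and 27 per arm, reproduces all four power figures: 80.1% and 36.1% (placebo 25%), 99.6% and 84.0% (placebo 40%). They concern the primary endpoint. No hazard ratio, event count or power is stated for the time-to-event analyses. Group B is expected to number about 54, so 27 per arm.

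**2. What each tie method estimates.** Let p0 and p1 be the probabilities that the event falls between two visits, given that it had not occurred before. When these are the same in every interval, the large-sample hazard ratios (HR) are:

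- Breslow: p1/p0
- exact-discrete: [p1/(1−p1)] / [p0/(1−p0)]
- interval-censored or complementary log-log: ln(1−p1)/ln(1−p0), the true HR

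Efron falls close to the third.

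**3. Group A.** The implied true HR is ln(0.95)/ln(0.75) = 0.178 for 25% vs 5%, and ln(0.95)/ln(0.60) = 0.100 for 40% vs 5%. Expected events are 55 × 0.30 = 16.5 and 55 × 0.45 = 24.75.

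| Visits | Placebo | Breslow | Efron | Exact-discrete | Interval-censored |
|---|---|---|---|---|---|
| 7, 14, 28 | 25% | 0.186 | 0.178 | 0.171 | 0.178 |
| 7, 14, 28 | 40% | 0.109 | 0.100 | 0.092 | 0.100 |
| all dated Day 28 | 25% | 0.200 | 0.179 | 0.158 | 0.178 |
| all dated Day 28 | 40% | 0.125 | 0.101 | 0.079 | 0.100 |

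On the Day 7/14/28 grid, tie handling moves the HR by about 0.01 from the truth, which is negligible with so few events.

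**4. Group B, Days 7 and 14 only, single-negative rule.** The documents give no clearance rate. Assume exponential clearance with placebo median 10 days and true HR 2. Over each 7 days p0 = 1 − exp(−7 ln2/10) = 0.384 and p1 = 1 − exp(−14 ln2/10) = 0.621, so Breslow tends to 0.621/0.384 = 1.62. Simulations of 27 per arm without frailty gave, over repeated runs:

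| Method | HR | Power |
|---|---|---|
| Breslow | 1.59–1.61 | 23–24% |
| Efron | 1.92–1.95 | 53–56% |
| Interval-censored Weibull | 2.02–2.04 | 56–58% |

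With Weibull shape 1.5 and median 8 days the same three gave HR 1.48, 1.86 and 2.09, and power 17%, 57% and 63%.

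Other assumed rates, large-sample. For 70% vs 90% cleared by Day 14, the true HR is ln(0.10)/ln(0.30) = 1.91. Two swabs give 1.51 (Breslow), 1.84 (Efron) and 2.62 (exact-discrete); all eight swabs give 1.78, 1.91 and 2.07. For 50% vs 70% (true 1.74), two swabs give 1.54, 1.72 and 1.99.

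**5. Group B, two-negative rule, equal swab supply (50% vs 70% by Day 14).** With Days 7 and 14 only, both must be negative, so clearance must precede Day 7: 1 − √0.5 = 29% and 1 − √0.3 = 45% count as cleared. With all eight swabs it must precede Day 13: 1 − 0.5^(13/14) = 47% and 1 − 0.3^(13/14) = 67%. At 27 per arm that is about 20 events instead of 31. The Efron HR stays at 1.68 to 1.78 against a true 1.74. Equal scarcity therefore costs events rather than adding much bias.

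**6. Group B, unequal supply (assumed).** With no true effect:

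| Rule | Optional swabs obtained | HR, visit day as event day | HR, interval-censored |
|---|---|---|---|
| Single negative | 80% vs 40% | 1.06–1.07 | near 1 |
| Single negative | 80% vs 20% | 1.15–1.17 | 1.02 |
| Two negatives | lambda 80%, placebo 40% | 1.19–1.23 | not tested |
| Two negatives | lambda 40%, placebo 80% | 0.80–0.81 | not tested |

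Under the two-negative rule at 27 per arm, Efron type I error was 4.4% and 4.8% with equal supply and 6.0% at 80% vs 40%, with a simulation standard error of about 0.8 points.

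**The case against.** The plan names neither Cox nor Breslow, and a frailty model can be fitted to grouped or interval-censored times. A reader might infer that visit days will be treated as exact event days; that is a reading of silence. It stands as an objection to that reading, but not to the gap itself.

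Most of the loss in step 4 comes from Breslow. Efron is within a few power points of the interval-censored model, so simply naming the tie method would remove most of it. That also stands, although Efron does not protect against unequal swabbing and does not date antibody-only infections.

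A reader might infer that swab shortages will create a spurious treatment effect. The documents describe no mechanism: both arms share one schedule, participants are blinded, and eight kits go home on Day 0 (section 10), enough for Days 2, 4, 6, 7, 9, 11, 13 and 14. Staff are not described as blinded, so arm-dependent sampling cannot be excluded, but it remains an assumption. The 6.0% type I error is not clear evidence of inflation.

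A reader might also infer that hospitalized participants are censored as if they cleared like the rest. No passage says so, and inpatient results from clinical care can be abstracted.

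Finally, these analyses supplement the primary one, Group B is an exploratory pilot, and time to infection is not a listed objective or secondary outcome. All true, and they limit the weight of the point.

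**Conclusion.** The point holds as a specification gap for which a better method is readily available. Both event times are interval-censored and the plan has no rule for this.

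- **Group B:** material. Under the step 4 assumptions, the unstated tie method alone moves the HR from about 1.6 to 1.94 and power from about 24% to 55%; an interval-censored model gives about 2.03 and 57%. Unequal supply would move a null HR to about 0.8 or 1.2 under the two-negative rule, but only if supply differed by arm.
- **Group A:** tie handling is negligible. Optional swabs do not arise there. What remains is how to date antibody-only infections.
- **Primary analysis:** unaffected, because the logistic model uses no event times.

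The Group B figures rest on assumed clearance rates and swab availability. Household frailty was not simulated, and the interval-censored model was not tested under the two-negative rule.

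**What to change.** In 13.2.1 and 13.2.2:

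1. Name an interval-censored or grouped-time (complementary log-log) proportional-hazards model for both outcomes, keeping the planned household random effect.
2. Define the interval as (last swab without the event, first swab showing it]. For clearance, state which of the two required negatives dates the event.
3. For antibody-only infections, use an interval from the last negative test to the serology date, and prespecify which test counts as the last negative.
4. State whether symptom-triggered clinical tests and abstracted inpatient PCR results count.
5. Reconcile Day 21 (12.1) with Day 28 (8.11).
6. Report the number of swabs obtained by arm.
7. Treat hospitalized participants without documented clearance as uncleared only in a sensitivity analysis.

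The cost is SAP wording, standard software and a little more analysis work, with no new data. A Weibull form would add a baseline-shape assumption; the grouped-time form avoids it.

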13.2.2 Analysis of Secondary outcomes including adverse events

For secondary time to event outcomes, we will perform survival analysis for time to infection in the prevention cohort and time to infection clearance in the treatment cohort, modeling within cluster correlation of hazard as a random effect (frailty).

Analysis of AE data will primarily be descriptive based on MedDRA coding of events. The proportion of participants experiencing an SAE and the proportion experiencing a Grade 3 or higher. AE will be compared between randomized arms using Fisher's Exact Test. Statistical analyses for the InFLUenza Patient-Reported Outcome (FLU-PRO[®]) measure of ordinal data of independent groups with more than three samples will utilize the Kruskal-Wallis H method.

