8.15. Adverse Event Evaluation

An AE is any untoward medical occurrence in a clinical study participant administered a medicinal (investigational or non-investigational) product. An AE does not necessarily have a causal relationship with the intervention. An AE can therefore be any unfavorable and unintended sign (including an abnormal finding), symptom, or disease temporally associated with the use of a medicinal (investigational or non-investigational) product, whether or not related to that medicinal (investigational or non-investigational) product (Definition per ICH).

This includes any occurrence that is new in onset or aggravated in severity or frequency from the baseline condition, or abnormal results of diagnostic procedures, including laboratory test abnormalities.

All adverse events, both serious and nonserious, will be collected from the time of informed consent through protocol Day 28. Participants will be asked open-ended and non-leading questions to evaluate for adverse events. Participants will also be asked directed questions to evaluate the presence or absence of fever, chills, arthralgia, myalgia, or pain. To monitor for injection site reactions, participants will be asked directed questions regarding pain, erythema, induration, or pruritus. The injection site will be inspected via video check-in on Day 7.

Adverse events will be collected directly in REDCap though a link embedded in the eMocha app. Participants will include their eMocha app username and cell phone number on the survey. For participants who are unable to access or use eMocha, surveys will be interviewer-administered over the phone by trained research staff.

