8.15.2 Serious Adverse Events

An SAE based on ICH and European Union Guidelines on Pharmacovigilance for Medicinal Products for Human Use is any untoward medical occurrence that at any dose:

- Results in death
- Is life-threatening
(The participant was at risk of death at the time of the event. It does not refer to an event that hypothetically might have caused death if it were more severe.)
- Requires inpatient hospitalization or prolongation of existing hospitalization
- Results in persistent or significant disability/incapacity
- Is a congenital anomaly/birth defect
- Is a suspected transmission of any infectious agent via a medicinal product
- Is Medically Important*

*Medical and scientific judgment should be exercised in deciding

whether expedited reporting is also appropriate in other situations, such as important medical events that may not be immediately life threatening or result in death or hospitalization but may jeopardize the participant or may require intervention to prevent one of the other outcomes listed in the definition above. These should usually be considered serious.

An exception to expedited reporting is progression of the disease under investigation; worsening of respiratory function due to COVID-19 requiring hospitalization will be reported as an adverse event but will not be reported as a SAE.

Any SAEs will be reported to the JHMIRB within 24 hours of the study team becoming aware of the event.

Initial reporting to the FDA: The Investigator/ designee will report any suspected adverse reaction or adverse reaction to study treatment that is both serious and unexpected.

Unexpected serious suspected adverse reactions and observations from animal studies suggesting significant risk to human subjects must be reported to FDA as soon as possible but no later than within 15 calendar days following the Investigator's initial receipt of the information.

Unexpected fatal or life-threatening suspected adverse reactions represent especially important safety information and must be reported to FDA as soon as possible but no later than 7 calendar days following the Investigator's initial receipt of the information.

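### In the Prevention Cohort, the Grade 3 or higher and treatment-emergent AE proportions mix COVID-19 illness with drug reactions, so the planned effect on infection attenuates any harm caused by Lambda

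*Combined protocol and SAP*

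**What the plan says.** Section 8.15 uses the broad ICH definition: "An AE does not necessarily have a causal relationship with the intervention". The collection period is the whole study: "All adverse events, both serious and nonserious, will be collected from the time of informed consent through protocol Day 28". This is also the window of the Prevention Cohort's infection endpoint. Some symptoms are actively solicited: "Participants will also be asked directed questions to evaluate the presence or absence of fever, chills, arthralgia, myalgia, or pain". Fever, chills and muscle pain are on the COVID-19 symptom screen in Section 8.1 as well.

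Section 13.2.2 first says: "Analysis of AE data will primarily be descriptive based on MedDRA coding of events". It then names two proportions for formal comparison: "The proportion of participants experiencing an SAE and the proportion experiencing a Grade 3 or higher", a sentence broken by a stray full stop, which continues "AE will be compared between randomized arms using" Fisher's exact test. The synopsis adds the proportion with treatment-emergent AEs (TEAEs) as a secondary outcome in each cohort. Section 13.2.2 names no test for that proportion.

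One provision treats COVID-19 separately. Under Section 8.15.2, "worsening of respiratory function due to COVID-19 requiring hospitalization will be reported as an adverse event but will not be reported as a SAE". Nothing in Section 13.2.2 divides COVID-19 events from others, or says whether Groups A and B are analysed apart.

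For the Prevention Cohort, Section 13.1 expects 25% to 40% infected on placebo and assumes in every scenario that "the cumulative infection fraction for the lambda interferon will be 5" percent.

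**The concern.** An AE total by arm measures net burden: events the drug causes plus illness it fails to prevent. If Lambda works as planned, the placebo arm carries the larger share of COVID-19 events. The better the drug prevents infection, the smaller the apparent excess of AEs on Lambda, whatever reactions it causes.

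Net burden is a legitimate quantity, but it is not the only one needed here. On the plan's own figures, 60% to 75% of the Prevention Cohort would stay uninfected even on placebo. For them the relevant safety question is what the injection itself does. The Grade 3 or higher test and the TEAE proportion do not answer that question when infection rates differ by arm, and no companion analysis is specified.

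**Working it through.** **Inputs from the documents.** Section 13.1: placebo infection p0 = 25% or 40%; Lambda infection 5%; about 110 in the Prevention Cohort (55 per arm) and about 54 in the Treatment Cohort (27 per arm); two-sided alpha 0.05. Section 4: about 15% of infected persons progress to severe pneumonia, used here as a proxy for the share s of infections giving a Grade 3 or higher AE.

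**Assumptions.** The documents give no Grade 3 or higher rate for Lambda or for other causes. I assume 2% from other causes in both arms, drug toxicity of 5% or 10%, and independent events and participants. The share s is also varied from 5% to 30%.

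**Step 1: the plan's own figures.** Exact power of the two-sided Fisher test at 5% versus 25% and 40% is 80.1% and 99.6% with 55 per arm, and 36.1% and 84.0% with 27 per arm. All four cells of the power table are reproduced. The table concerns infection, not AEs, but this confirms the infection rates, and the same enumeration is used in Step 3.

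**Step 2: Grade 3 or higher offset, Prevention Cohort.** Offset = (p0 − 0.05) × s. At s = 15%:
- 25% row: 0.25 × 0.15 = 3.75% on placebo, 0.05 × 0.15 = 0.75% on Lambda; offset 3.0 points.
- 40% row: 0.40 × 0.15 = 6.0% against 0.75%; offset 5.25 points.

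At s = 5% the offsets are 1.0 and 1.75 points; at s = 30%, 6.0 and 10.5 points.

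**Step 3: effect on the test, 55 per arm, s = 15%.** With COVID-19 events pooled in, placebo = 1 − 0.98 × (1 − 0.15 p0), and Lambda = 1 − 0.98 × (1 − t) × (1 − 0.0075) for toxicity t. With them separated, placebo = 2% and Lambda = 1 − 0.98 × (1 − t).

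| Toxicity t | Analysis | Expected difference (points) | Chance of significant harm |
|---|---|---|---|
| 10% | separated | +9.8 | 36% |
| 10% | pooled, 25% row | +6.8 | 13% |
| 10% | pooled, 40% row | +4.6 | 6% |
| 5% | separated | +4.9 | 7% |
| 5% | pooled, 25% row | +1.9 | 2% |
| 5% | pooled, 40% row | −0.3 | 0.7% |

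The chance falls for two reasons: the difference shrinks, and the background rate rises.

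**Step 4: any-grade TEAEs.** Now let s be the share of infections producing any AE. The documents do not give it, so 30% to 90% is assumed. The drug-caused rate t that leaves the arms equal solves 0.05s + t(1 − 0.05s) = p0 s, so t = (p0 − 0.05)s / (1 − 0.05s).
- s = 30%: 0.06/0.985 = 6.1% (25% row); 0.105/0.985 = 10.7% (40% row).
- s = 60%: 0.12/0.97 = 12.4%; 0.21/0.97 = 21.6%.
- s = 90%: 0.18/0.955 = 18.8%; 0.315/0.955 = 33.0%.

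**Step 5: Treatment Cohort.** These participants are infected at entry, so no infection is prevented and this offset does not arise. If the cohorts were analysed together, the Step 2 offsets would dilute to 3.0 × 55/82 = 2.0 and 5.25 × 55/82 = 3.5 points.

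**The case against.** A reader might infer that the AE comparisons as a whole would cancel Lambda's toxicity and make an unsafe drug look safe. The documents do not support that, for five reasons.

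- **SAEs.** Section 8.15.2 keeps hospitalization for COVID-19 respiratory worsening from being reported as an SAE. That takes the main COVID-19 component out of one of the two tested proportions. The sentence opens as an exception to expedited reporting, so its reach into the analysis is unclear.
- **Which proportion is tested.** The large figures in Step 4 concern any-grade events, for which Section 13.2.2 names no test. They also rest on an assumed share; infection under Section 12.1 includes cases found only by swab or serology, which need not produce any AE. For the tested Grade 3 or higher proportion, the offset is a few points.
- **Term-level tables.** The main AE analysis is descriptive by MedDRA coding. Injection-site reactions and hepatobiliary toxicity, the identified risks in Section 11, are not on the Section 8.1 symptom list, so COVID-19 would not hide them there. (Section 8.13 names Day 0 only for the metabolic panel, so a missing transaminase signal could reflect lack of measurement, not pooling.) Section 8.15.1 also provides for a causality assessment.
- **Treatment Cohort.** About a third of participants contribute no offset of this kind.
- **Validity.** The all-events comparison is a sound randomized estimate of net burden.

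All five limit the claim, but none removes it. The SAE exception keeps the hospitalizations as AEs, so they can still enter the Grade 3 or higher count. MedDRA tables cannot sort overlapping terms such as fever and myalgia by cause. The causality call is not used in Section 13.2.2, and Section 9.4 states blinding for participants only.

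**Conclusion.** The point holds for two measures in the Prevention Cohort: the Grade 3 or higher comparison and the TEAE proportion. Both are biased toward showing no harm if Lambda prevents infection as planned, and no pre-specified analysis corrects for this.

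For Grade 3 or higher events, drug toxicity up to about 3.0 to 5.25 points is cancelled and larger toxicity is attenuated. This rests on the 15% severe share as a proxy. For TEAEs, a drug-caused rate of about 6% to 19% (25% row) or 11% to 33% (40% row) could be hidden, depending wholly on the assumed share of infections that produce an AE. The SAE comparison is less affected.

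The gap is a missing companion analysis, not an invalid test. Low power is a separate limit: under the Step 3 assumptions, a true 10% Grade 3 or higher toxicity would be detected only 36% of the time even with COVID-19 events separated.

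**What to change.** In Section 13.2.2, keep the all-events comparison and label it as the net effect. Add two tables, separately for Groups A and B, with all randomized participants of the group in the denominator and with risk differences and 95% confidence intervals:

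- **(a) Early onset.** TEAE and Grade 3 or higher proportions with onset in a pre-specified window after dosing, such as Days 0 to 3. The window length is an assumption, and some infections already incubating at entry may still surface in it.
- **(b) Event type.** TEAE and Grade 3 or higher proportions split into COVID-19-type and other events by a MedDRA term list fixed in advance. The list is applied identically in both arms, without reference to arm or infection status.

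Do not restrict to uninfected participants, and do not anchor exclusions to the first positive test. Infection is a post-randomization outcome expected to differ by arm. In Group B such an anchor falls at Day 0, and an infection found only by Day 28 serology would be mistimed.

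State also whether the Section 8.15.2 exception governs the SAE analysis or only reporting.

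The cost is SAP wording and two tables from data already collected. Table (a) will miss late drug reactions, table (b) will misclassify some overlapping symptoms such as fever and myalgia, and power stays low.
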